## 1.2. Study Design

This study is a randomized, double-blind, placebo controlled, multicenter, Phase 2b study to evaluate the efficacy and safety of 3 active dose regimens of MORF-057 (as capsule, P.O.) versus matching placebo in study participants with moderately to severely active UC.

Approximately 280 participants will be randomized into the treatment groups in a 1:1:1:1 ratio (i.e., 70 participants per group). The study will enroll participants who are advanced therapy naïve (i.e., have no previous exposure to an advanced therapy treatment for UC) and advanced therapy experienced (excluding vedolizumab), with at least 30% but no more than 40% of advanced therapy experienced participants. Randomization stratification factors will include baseline MES (<3 vs 3) and previous use of advanced therapy treatment (advanced therapy naïve vs advanced therapy experienced). All participants will be enrolled from approximately 150 centers worldwide. For this study, moderately to severely active UC will be defined as having an mMCS of 5 to 9 (inclusive), with an MES  $\geq 2$  (confirmed by central reader).

The main part of this Phase 2b study will consist of a Screening Period (up to 6 weeks, consisting of Stage 1 and Stage 2 testing), a Treatment Period (52 weeks, including a 12-week Induction Period and a 40-week Maintenance Period), and a Safety Follow up (SFU) Period (4 weeks).

During the main part of this study, there will be approximately 11 scheduled study visits: Screening Visit(s) (Visit 1 at Weeks 6 to 1), multiple Treatment Visits (Visits 2-10 at Weeks 0, 2, 6, 12, 18, 24, 32, 42, and 52 [End of Treatment (EOT)]), and an SFU Visit (visit to occur 4 weeks after the last dose of study drug is received, which will be at Week 56 if the full Treatment Period is completed or earlier if treatment is discontinued early). Study Day 1 represents the first day of the Treatment Period (i.e., when the participant will receive the first dose of study drug).

All participants who complete the 52-week Treatment Period will have the opportunity to continue their treatment in a 52-week Maintenance Extension Period.

During the optional Maintenance Extension, there will be 5 scheduled visits: 4 Treatment Visits (Visits 11-14 at Weeks 65, 78, 91, and 104 [EOT]) and an SFU Visit (visit to occur 4 weeks after the last dose of study drug is received, which will be at Week 108 if the full Maintenance Extension is completed or earlier if treatment is discontinued early).

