### 1.3. Sample Size and Power

The sample size was determined based on the primary endpoint of clinical remission at Week 12 by using the Chi-Squared Test to compare two proportions. A sample size of 70 participants per group (giving a total of 280) will provide 80% power to detect a difference of 15% in the clinical remission rate between MORF-057 and placebo, based on the use of a two-sided test at the alpha=0.10 level of significance. The calculation is based upon an assumed placebo remission rate of 7%.

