#### 4.8.1.1. Primary Efficacy Analysis

The clinical remission rate at Week 12 will be analyzed for FAS using a two-sided Cochran-Mantel-Haenszel (CMH) test at 10% level of significance, stratified by randomization stratification factors (baseline MES [ $<3$  vs  $3$ ] and previous use of advanced therapy treatment [advanced therapy-naïve vs advanced therapy-experienced]), for comparison of each MORF-057 dose group with the placebo group. The p-values will be provided. The point estimates of risk difference between groups with both 95% and 90% confidence intervals (CIs) will also be computed based on the stratified risk difference using the Cochran-Mantel-Haenszel (CMH) weights (see the method in Section 6.5). All participants with missing data for determination of endpoint status will be considered as a nonresponder by using the NRI method.

The study will be considered as a success if at least one MORF-057 dose achieves the statistical significance at the specified significant level after the multiplicity adjustment as specified in Section 4.8.6.

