#### 4.8.2. Secondary Efficacy Endpoint Analysis

The secondary endpoint for this study is the proportion of participants with clinical response at Week 12 as determined using the mMCS: decrease from baseline in the mMCS  $\geq 2$  points and  $\geq 30\%$  from baseline, plus a decrease in rectal bleeding subscore  $\geq 1$  or an absolute rectal bleeding subscore  $\leq 1$ .

The clinical response rate will be analyzed based on FAS using CMH method stratified by randomization stratification factors (baseline MES [ $<3$  vs  $3$ ] and previous use of advanced therapy treatment [advanced therapy-naïve vs advanced therapy-experienced]) for comparison of each MORF-057 dose group with the placebo group, similar to the primary analysis performed for the primary endpoint. The p values will be provided. The point estimates of risk difference between groups, along with both 90% and 95% CIs will be computed based on the stratified risk difference using the Cochran-Mantel-Haenszel (CMH) weights. All participants with missing data for determination of endpoint status will be considered as a non responder in the analysis by using the NRI method.

Morphic Therapeutic, Inc.  
Study Number: MORF-057-202

Statistical Analysis Plan  
Version 1.0, 16SEP2024

Sensitivity analysis will be performed by repeating the secondary efficacy analysis using the PP Population. Additionally, another sensitivity analysis will compare the combined MORF-057 200 BID and 100 BID dose groups with the placebo group for FAS.

Furthermore, if there is any discrepancy between the randomization stratum reported in the IRT and the actual stratum the participant belongs to, a sensitivity analysis for the secondary endpoint will be performed using CMH method stratified by the randomization stratum reported in the IRT based on FAS.

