## 6.5. The Calculation of Stratified Risk Difference Between Two Groups Using the Cochran-Mantel-Haenszel (CMH) Weights

Suppose that participants are randomly assigned into the active group or placebo group, stratified by K factors ( $K \geq 2$ ):

Strata	Response	Active Group	Placebo	Total
1	Yes	$x_{11}$	$x_{01}$	$x_1$
	No	$n_{11}-x_{11}$	$n_{01}-x_{01}$	$n_1-x_1$
	Total	$n_{11}$	$n_{01}$	$n_1$
2	Yes	$x_{12}$	$x_{02}$	$x_2$
	No	$n_{12}-x_{12}$	$n_{02}-x_{02}$	$n_2-x_2$
	Total	$n_{12}$	$n_{02}$	$n_2$
...				
K	Yes	$x_{1K}$	$x_{0K}$	$x_K$
	No	$n_{1K}-x_{1K}$	$n_{0K}-x_{0K}$	$n_K-x_K$
	Total	$n_{1K}$	$n_{0K}$	$n_K$

Morphic Therapeutic, Inc.  
Study Number: MORF-057-202

Statistical Analysis Plan  
Version 1.0, 16SEP2024

$n_{1j}$  is the number of participants randomized to the active group and  $x_{1j}$  is number of responders in the active group for strata j, and  $n_{0j}$  is the number of participants randomized to placebo and  $x_{0j}$  is number of responders in the placebo group for strata j.

The response rate difference  $\delta_j = p_{1j} - p_{0j}$  between active group and placebo for strata j is estimated by

$$\widehat{\delta}_j = \widehat{p}_{1j} - \widehat{p}_{0j}$$

Where the estimated response rate  $\widehat{p}_{1j} = x_{1j} / n_{1j}$  and  $\widehat{p}_{0j} = x_{0j} / n_{0j}$ .

The overall response rate difference is estimated by the stratified response rate difference using the CMH weights, which is calculated as

$$\widehat{\delta}_w = \sum_{j=1}^K w_j \widehat{\delta}_j$$

where  $w_j = (n_{1j}^{-1} + n_{0j}^{-1})^{-1} / [\sum_{j=1}^K (n_{1j}^{-1} + n_{0j}^{-1})^{-1}]$  is the weight for stratum j with  $\sum_{j=1}^K w_j = 1$ .

The 100  $(1 - \alpha)\%$  confidence interval of the overall response rate difference is given by

$$\widehat{\delta}_w \pm Z_{\alpha/2} \sqrt{\sum_{j=1}^k w_j^2 \widehat{V}(\widehat{\delta}_j)}$$

Where  $\widehat{V}(\widehat{\delta}_j) = (\widehat{p}_{1j}(1 - \widehat{p}_{1j})/n_{1j}) + (\widehat{p}_{0j}(1 - \widehat{p}_{0j})/n_{0j})$  is the estimated variance of the response rate difference in strata j and  $Z_{\alpha/2}$  is the  $(1 - \alpha/2)$  percentile of the standard normal distribution.

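### The Section 6.5 intervals for the primary and secondary risk differences are slightly too narrow and do not match the CMH test reported beside them

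*SAP*

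**What the plan says.** For the primary endpoint, SAP Section 4.8.1.1 tests each dose against placebo with a two-sided CMH test stratified by baseline MES and prior advanced therapy (2 x 2 = 4 strata). It adds: "The point estimates of risk difference between groups with both 95% and 90% confidence intervals (CIs) will also be computed". Section 4.8.2 does the same for clinical response: "The point estimates of risk difference between groups, along with both 90% and 95% CIs will be computed".

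Section 6.5 gives the formula for these intervals. The point estimate is the CMH-weighted average of the stratum differences. The interval is a Wald interval whose stratum term, p1(1-p1)/n1 + p0(1-p0)/n0, "is the estimated variance of the response rate difference in strata j".

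Section 1.3 plans with a "two-sided test at the alpha=0.10 level of significance" and states that 70 per group "will provide 80% power to detect a difference of 15% in the clinical remission rate", from an assumed placebo rate of 7%. Under Sections 4.8.1.1 and 4.8.6, success rests on p-values through Hochberg and the fixed sequence. The intervals play no part in that decision.

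**The concern.** The estimate in Section 6.5 is proportional to the numerator of the CMH statistic, so the test and the interval in one table row differ only in their variance. Section 6.5 uses an unpooled variance with divisor n. In strata of perhaps 12 to 23 per arm, that divisor makes the estimated variance too small on average. Two things follow. The interval covers less than its nominal level. It can also exclude zero in a row where the CMH p-value does not reach the matching level, which leaves the study report to explain a conflict that the plan built in. These intervals are the only statement of uncertainty about the effect size that the plan specifies for the primary and secondary comparisons.

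**Working it through.** **Inputs.** From the SAP: 70 per arm, 1:1:1:1 (Sections 1.2, 1.3); 7% vs 22%, two-sided alpha 0.10 (1.3); four strata, with 30-40% advanced-therapy experienced (1.2). Assumed, because the SAP does not give them: the share with MES 3 (50%, 65% and 85% tried), response rates for the secondary endpoint (30% vs 45%, 35% vs 50%), intermediate remission rates, and near-equal arms within strata.

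**1. The plan's own figure.** n = [1.645 x sqrt(2 x 0.145 x 0.855) + 0.842 x sqrt(0.22 x 0.78 + 0.07 x 0.93)]^2 / 0.15^2 = (0.819 + 0.409)^2 / 0.0225 = 67.1, so 68 per group. Power at 70 per group is 81.5%. The stated 70 and 80% are reproduced. The SAP states no coverage figure.

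**2. The two variances.** Both use the same weights w_j. With m per arm in a stratum, pbar the pooled rate and d the difference:
- Section 6.5: (2/m) x [pbar(1-pbar) - (d/2)^2]
- CMH: (2/m) x pbar(1-pbar) x 2m/(2m-1)

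With equal arms in each stratum the first is always the smaller.

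**3. Expected size.** Put w_j = m_j/70 and take expectations.
- No difference between arms: the Section 6.5 variance is proportional to the sum of (m_j - 1) = 70 - 4 = 66, and the CMH variance to the sum of m_j = 70. The SE ratio is sqrt(66/70) = 0.971, whatever the mix of strata.
- 22% vs 7%: Section 6.5 gives 66 x (0.1716 + 0.0651) = 15.62. CMH gives 70 x 2 x 0.123975 + 0.0232 = 17.38, where 0.0232 is the sum over four strata of (d/2)^2 x m/(m - 0.5), at m = 17.5. The SE ratio is sqrt(15.62/17.38) = 0.948.

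The gap has two parts. The factor 66/70 is a downward bias relative to the true variance, and it is what costs coverage. The remainder, 0.948/0.971 = 0.976, is the ordinary difference between pooled and unpooled variances. It affects agreement with the test but is not an error in the interval.

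**4. Coverage by approximation.** In simulation the planned SE averages about 3-4% below the true SD. Taking 0.965 as the ratio, 2 x Phi(1.645 x 0.965) - 1 = 88.8% and 2 x Phi(1.96 x 0.965) - 1 = 94.1%.

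**5. Simulation.** 200,000 trials per scenario, 70 per arm, 35% experienced, 50% MES 3. Cells in the last two columns are the share of all trials, with the share of failed tests in brackets.

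| Active vs placebo | Coverage 90% / 95% | Coverage with n-1, 90% / 95% | 90% CI excludes 0, CMH p >= 0.10 | 95% CI excludes 0, CMH p >= 0.05 |
|---|---|---|---|---|
| 7% vs 7% | 88.5 / 93.8 | 89.2 / 94.8 | 1.0% (1.1%) | 1.5% (1.5%) |
| 17% vs 7% | 88.6 / 94.0 | 89.7 / 94.7 | 2.1% (5.1%) | 3.3% (6.0%) |
| 22% vs 7% | 88.5 / 93.9 | 89.6 / 94.6 | 1.4% (8.4%) | 2.6% (9.7%) |

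The reverse, with CMH rejecting while the interval includes zero, was 0.0% in these runs and about 0.1% or less in any run. Across other stratum mixes and the assumed response rates, coverage was 88.4-88.9% and 93.7-94.2%, and disagreement roughly 0.3-3.6% of trials. The largest disagreement was in a scenario away from the planning rates (3% vs 13%): 4.4% of trials and 11.5% of failed tests at the 95% level. At a 3% rate in both arms the 95% interval did not under-cover (95.1-95.3%).

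**The case against.** The strongest reply is that Section 6.5 contains no contradiction. It fully specifies a familiar large-sample interval. Pairing a test that uses the null variance with an interval that uses the unpooled variance is legitimate, since the unpooled form suits a non-zero difference. The loss is about 1 to 1.5 points of coverage in a Phase 2b table column that decides nothing. All of that stands, and it limits the weight of the point. It does not remove the divisor bias, which is a shortfall in the interval itself and cheap to correct.

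A reader might infer four stronger things that the documents and calculations do not support.
- *The interval will often contradict a failed test.* At the planning rates, about nine in ten failed tests or more agree with it.
- *A near miss will usually be contradicted.* This depends on how narrowly a near miss is defined. For p of 0.10-0.12 the 90% interval excluded zero in anything from 18% to 63% of cases, depending on stratum and rate assumptions, and such p-values arise in only about 2-4% of trials. For p of 0.10-0.15 it was 24-32%. For p of 0.05-0.06 the 95% interval did exclude zero in 65-92% of cases, but for 0.05-0.075 mostly in 38-44%.
- *The interval is biased towards an effect.* It is symmetric about an unchanged estimate. Under no difference, misses of the 90% interval were balanced (5.7% vs 5.8%). At 22% vs 7% it lay below the true effect more often than above it (6.3% vs 5.2%). Only the disagreement with the p-value runs one way.
- *Correcting the variance reconciles the 90% interval with Hochberg.* The 90% interval excludes zero while a B.I.D. dose fails Hochberg in 3.7-8.1% of trials, but 2.4-6.9% of trials would show this with the CMH variance too, because Section 4.8.6 can require p < 0.05. That is a separate multiplicity matter.

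**Conclusion.** The point holds as one of reporting. The intervals for both headline endpoints rest on a standard error about 3-5% below that of the accompanying CMH test. About 3 percentage points of that gap is downward bias from dividing by n in each of four strata. At the planning rates the 90% interval covers about 88.5-89% and the 95% interval about 94%, with occasional one-way disagreement with the test. Type I error, power and the success rule are untouched.

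The expected SE ratio under no difference needs only the 70 per arm, four strata and equal arms within strata. The coverage and disagreement figures also rest on the assumed MES split and, for clinical response, on assumed rates; they changed little across the stratum mixes tried.

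**What to change.** In Section 6.5, keep the CMH-weighted point estimate and replace the interval with the stratified Miettinen-Nurminen score interval using the same weights. At a difference of zero its variance is the pooled one with factor N/(N-1), so its statistic equals the CMH statistic. The 90% (95%) interval then excludes zero exactly when the unadjusted CMH p-value is below 0.10 (0.05). Simulated coverage was 90.0-90.4% and 95.0-95.4%.

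If a closed form is preferred, write n1-1 and n0-1 in place of n1 and n0 in each stratum variance. Coverage returns to about 89-90% and 94.6-94.9%, but agreement with the test is then only approximate. At the planning rates the remaining disagreement was 0.1-0.6% of trials for the 90% interval and 0.2-1.0% for the 95% interval.

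Under either option, add one sentence saying that the multiplicity-adjusted p-value governs and that the intervals are not adjusted for Hochberg. The change also carries over to Sections 4.8.3.1 and 4.8.4, which report the same weighted difference.

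The cost is a few lines of text, standard software and slightly wider intervals. The test, the estimate and the sample size stay as they are.
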